8.10. PTC Therapeutics Adverse Event Reporting Requirements

As the sponsor of the study, PTC Therapeutics is responsible for reporting certain safety information, particularly SAEs and subject deaths related to participation in the study, to each investigator in an expedited manner. If notification of an adverse event requiring expedited reporting to investigators is received, PTC Therapeutics or its designated representative will contact each investigator site participating in this study by e-mail, fax, and/or overnight mail such that the investigator can promptly notify the site IRB/IEC per their local requirements. The initial expedited safety report will be provided as required according to local regulations (eg, within 15 days) after the earliest date PTC Therapeutics or an agent of PTC Therapeutics (eg, a site monitor) becomes aware of an adverse event. This awareness date is the date the regulatory reporting clock begins and the date is considered Day 0.

9. WITHDRAWAL OF PATIENTS

All patients who receive ataluren should remain in the study whenever possible. Treatment with ataluren in the context of this protocol is anticipated to occur for 240 weeks. The actual duration of ataluren treatment under this protocol will be subject to the following conditions:

- The patient has the right to withdraw consent and discontinue ataluren at any time.
- If the patient's condition substantially worsens after initiating ataluren treatment, the patient
 will be carefully evaluated by the investigator in consultation with the PTC Therapeutics
 medical monitor. This worsening may include cardiac events such as QTc interval limits,
 new evidence of symptomatic cardiomyopathy and significant decrease in left ventricular
 ejection fraction. The patient will be withdrawn from treatment if continuing would place
 them at risk.
- Upon consultation with the PTC Therapeutics medical monitor, the investigator may withdraw the patient from ataluren treatment, if, in the investigator's clinical judgment, it is not in the patient's best interest to continue.
- The patient will be withdrawn from treatment if he is unable to tolerate ataluren.
- The patient may be withdrawn from this study if he is eligible to participate in another ataluren - nmDBMD clinical study or program.
- This study may be discontinued by the relevant regulatory authority and/or PTC Therapeutics at any time.
- This study may be stopped upon ataluren marketing authorization within the relevant country.

The date study treatment is discontinued and the reason for discontinuation will be recorded in the source documents and in the eCRF. The MAPI medical monitor and the PTC medical monitor should be informed via e-mail of when a subject is discontinues study treatment.

When study treatment is discontinued, (regardless of the reason), the investigator should encourage that all of the evaluations required at the End of Treatment Visit be performed and that any additional evaluations be completed that may be necessary to ensure that the patient is free of untoward effects. The patient should be encouraged to seek appropriate follow-up for any continuing health problems.

10. STATISTICS AND DATA MANAGEMENT

10.1. Sample Size Calculation for the Primary Endpoint

The pool of patients potentially eligible for this study is described by inclusion criterion 2 of Section 4.2. Hence the sample size is determined by how many such patients satisfy all inclusion/exclusion criteria when applying for participation in this study and not by any formal statistical hypothesis.

10.2. Study Population Definition

10.2.1. As-Treated Population

The as-treated population consists of all patients who receive at least 1 dose of ataluren. This population will be evaluated in the analyses of safety (the primary endpoint) and treatment administration.

10.3. General Statistical Considerations

By-patient listings will be created for each CRF module.

Summary tables for continuous variables, overall and by corticosteroid use, will contain the following statistics: n, mean, standard deviation, standard error, 95% confidence intervals (CIs) on the mean, median, minimum, and maximum. In addition, changes from baseline will be likewise summarized.

Summary tables for categorical variables, overall and by corticosteroid use, will include N, n, and percentages.

In addition to a stand-alone analysis of data from this study, the data may be interpreted in conjunction with corresponding data from other alaluren studies.

10.4. Specific Statistical Analyses

10.4.1. Study Conduct and Subject Disposition

Subjects who discontinue at luren prematurely or are removed from the study prematurely will be reported. Reasons for screening failures and early discontinuations, and time of withdrawal from study will be described.

10.4.2. Baseline Characteristics

Subject characteristics at entry into the study will be summarized in frequency tables and descriptive statistics will be provided for quantitative variables.

10.4.3. Study Treatment Administration

For each patient, ataluren administration will be described in terms of the total duration of therapy, dose modifications, dose delays, and dose omissions; and reasons for deviations from planned therapy.

10.4.4. Use of Concomitant Medication and Supportive Therapy

Concomitant medications will be coded using the World Health Organization Drug Dictionary (WHODRUG) dictionary into Anatomical-Therapeutic-Chemical classification (ATC) codes. The type and timing of use of specific concomitant medications will be listed and summarized.

Specific attention will be focused on corticosteroid use and use of drugs for prophylaxis/treatment of CHF. The type and duration of pre-study use will be described. The type, dose, schedule, duration of use, dose modifications, dose omissions, and reasons for deviations from initial therapy will be described.

10.4.5. Primary Variables

10.4.5.1. Adverse Events

Adverse events will be classified using the MedDRA classification system. The severity of adverse events will be graded by the investigator according to the CTCAE, Version 3.0 whenever possible. A treatment-emergent adverse event is defined as an adverse event that occurs or worsens in the period extending from the day of a patient's first ataluren dose in this study to 6 weeks after the last ataluren dose in this study.

The frequency of patients experiencing a specific adverse event will be tabulated by visit, body system, and MedDRA term. In the by-patient analysis, a patient having the same event more than once will be counted only once using the worst CTCAE grade.

Adverse events classified as CTCAE Grade 3 or higher; study-drug-related events; adrenal, hepatic, and renal events leading to special diagnostic evaluations; events leading to discontinuation from treatment; and SAEs will be considered with special attention.

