1 OVERVIEW

This statistical analysis plan (SAP) details the statistical methods to be used in the analyses and presentation of the data collected in Study PTC124-GD-019-DMD, also referred to as Study 019. Preparation of this SAP incorporates statistical design elements present in the protocol Version 5.0 (dated 18 November 2015). Details are documented in Sections 1-7.

In addition to the protocol defined analyses, a natural history control using the Cooperative International Neuromuscular Research Group (CINRG) will be utilized in order to help to better understand the long-term ataluren data. The planned analysis will be presented in Section 8.

After the implement of protocol Version 5.0, the sponsor has developed the protocol Version 6.1 (dated 08 March 2017) specifically for Canadian sites only for ethics approval when they finished all visits per Version 5.0 and were waiting to roll into another open-label nmDMD Study PTC124-GD-016-DMD conducted in the United States (US). The maximal scheduled visit in Version 5.0 was extended from week 240 to week 336 in Version 6.1. All data collected based on both Versions will be summarized together.

Where conflicts exist between this SAP and the study protocols, the information contained in this SAP supersedes the protocol.

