3.3 Study Endpoints

Primary:

- Safety profile characterized by type, frequency, severity, timing, and relationship to ataluren of any adverse events or laboratory abnormalities

Secondary:

- In ambulatory subjects,
 - i. change from baseline in 6MWD as measured by the 6-minute walk test (6MWT)
 - ii. change from baseline in physical function as measured by the North Star Ambulatory Assessment (NSAA)
 - iii. change from baseline in timed function tests (time to stand from supine and time to run/walk 10 meters)
- In non-ambulatory subjects,
 - i. change from baseline in pulmonary function test - % predicated forced vital capacity (FVC) and % predicted forced expiratory volume in 1 second (FEV1) as measured by spirometry
 - ii. change from baseline in patient and parent/caregiver-reported activities of daily living, as measured by the Egen Klassifikation (EK) scale

- All subjects,
 - i. changes in patient and/or parent/caregiver reports of disease status as measured by a standardized survey administered by site personnel

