5.7 Primary Variables

5.7.1 Adverse Events

Adverse events will be classified using MedDRA Version 20.1 classification system. The severity of adverse events will be graded by the investigator according to the CTCAE, Version 3.0 whenever possible. A treatment-emergent adverse event (TEAE) is defined as an adverse event that occurs or worsens in the period extending from the day of a subject's first dose of study drug to 6 weeks after the last dose of study drug in this study.

If a subject has multiple events under any given SOC and PT, the subject will be counted only once under that SOC and PT. If a subject has the same AE on multiple occasions, the highest severity (fetal, life-threatening, severe, moderate, and mild) recorded for the event will be presented and the highest drug relationship (1 = 'Unrelated', 2 = 'Unlikely', 3 = 'Possibly', 4 = 'Probably', 5 = 'Related'), reclassified into Related ('Possibly Related', 'Probably Related', 'Related') or Not Related ('Unrelated' and 'Unlikely'), will be presented on the respective tables.

Total numbers of AEs, TEAEs and serious AEs (SAE) and the number and percentage of subjects experiencing ≥ 1 TEAE, ≥ 1 SAE, discontinuation due to AE, and death will be tabulated. The number and percentage of subjects with TEAEs and SAEs will be by relationship to study drug and CTCAE/severity, respectively.

The number and percentage of subjects experiencing a specific TEAE will be tabulated

- by SOC, and PT
- by SOC, PT, and CTCAE/severity grade
- by SOC in the descending order of the SOC frequency in ataluren group
- by PT in the descending order of the PT frequency in ataluren group.

The following TEAEs will be analyzed similarly:

- by SOC, and PT and
- by SOC, PT, and CTCAE/severity grade.
 - i. Possibly or probably treatment-related TEAEs
 - ii. Possibly treatment-related TEAEs
 - iii. Probably treatment-related TEAEs
 - iv. Serious TEAEs and possibly or probably treatment-related serious TEAEs
 - v. TEAEs leading to discontinuation from treatment
 - vi. Hepatic and renal TEAEs and possibly or probably treatment-related hepatic and renal TEAEs leading to special diagnosis evaluation
 - vii. TEAEs with CTCAE/severity grade ≥ 3 and possibly or probably treatment-related TEAEs with CTCAE/severity grade ≥ 3
 - viii. Common TEAEs (subject frequency of $\geq 5\%$)

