Listings of death, serious AEs, AEs leading to discontinuation from treatment, and hepatic and renal AEs leading to special diagnostic evaluations will be provided.

The drug exposure adjusted TEAE incidence rate will be summarized by SOC and PT, where the incidence rate of the TEAE per 100 patient-year = (number of events/number of patient-years) *100. The number of patient-years is defined as the sum of the number of days on study drug of all patients divided by 336. That is, a year is defined as 48 weeks.

In addition, the number of subjects with clinical laboratory abnormalities, abnormal vital signs, and abnormal electrocardiogram reported as TEAE will be summarized.

Non-serious TEAE will be displayed by SOC and PT. The common non-serious TEAE (subject frequency of $\geq 5\%$) will also be displayed by SOC and PT.

Numbers of occurrence of serious TEAE and the numbers of occurrence of non-serious TEAE will be summarized by SOC and PT, separately.

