7 ANALYSIS CHANGES FROM PROTOCOL

The paired t-test is removed from the analysis on change from baseline in 6-minute walk test, timed function tests, North Star Ambulatory Assessment, Egen Klassifikation Scale, and spirometry endpoints. Subgroup analyses based on 6-minute walk test, corticosteroid type, and the cumulative duration of corticosteroid use are added.

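### The SAP leaves out the protocol's by-visit adverse event table without recording the change, so the timing of adverse events, part of the primary endpoint, has no aggregate summary

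*Protocol*

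**What the plan says.** SAP section 3.3 repeats the protocol's primary endpoint (protocol section 3.3): "Safety profile characterized by type, frequency, severity, timing, and relationship to ataluren of any adverse events or laboratory abnormalities". Protocol section 10.4.5.1 gives the AE part a time dimension: "The frequency of patients experiencing a specific adverse event will be tabulated by visit, body system, and MedDRA term".

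SAP section 5.7.1 sets out its own tables. "The number and percentage of subjects experiencing a specific TEAE will be tabulated" introduces four cuts: SOC and PT; "by SOC, PT, and CTCAE/severity grade"; SOC in order of frequency; and PT in order of frequency. The same kinds of table follow for treatment-related, serious, Grade 3 or higher, hepatic and renal, common and discontinuation-related events. One summary is added: "The drug exposure adjusted TEAE incidence rate will be summarized by SOC and PT", with this denominator: "The number of patient-years is defined as the sum of the number of days on study drug of all patients divided by 336".

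SAP section 7, on changes from the protocol, begins "The paired t-test is removed from the analysis on change from baseline in 6-minute walk test". It goes on to the other secondary endpoints and to added subgroups, and says nothing about AE tables. SAP section 1 states: "Where conflicts exist between this SAP and the study protocols, the information contained in this SAP supersedes the protocol".

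**The concern.** The primary objective is long-term safety over a planned 240 weeks, extended to Week 336 for Canadian sites under protocol Version 6.1 (SAP section 1). In such a study it matters whether an event clusters early and fades or keeps accruing. The protocol gives its own reasons to ask. Section 13.2.3.2.1 reports adrenal findings in dogs dosed for 20 weeks or more that had not reversed by the end of recovery. Section 14.3 describes earlier AEs as mostly transient. A whole-study percentage and a pooled rate could neither support nor contradict a statement of that kind for AEs in this study. The omission is also unrecorded, so a reader of section 7 would not know that a protocol table for the primary endpoint is missing.

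**Working it through.** The plan states no figure to reproduce; sample size is set by availability (protocol section 10.1). The check has three parts.

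**1. Which AE outputs use time?**

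| Output | Place | Uses AE onset time? |
|---|---|---|
| AE frequency by visit, body system, term | Protocol 10.4.5.1 | Yes, by visit |
| TEAE tables by SOC, PT, severity, relationship, seriousness | SAP 5.7.1 | No |
| Exposure-adjusted TEAE rate | SAP 5.7.1 | No, pooled over follow-up |
| Listings by patient and of selected AEs | SAP 5.1, 5.7.1 | Dates shown, not summarised |
| Kaplan-Meier time to discontinuation | SAP 5.2 | No, AE discontinuations not separated |
| Kaplan-Meier age at loss of ambulation | SAP 5.8.2 | Uses a disease-progression AE, but as an efficacy event on the age scale |
| Laboratory, vital signs, ECG | SAP 5.7.2 to 5.7.4 | By visit, but not AEs |

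**2. Can the exposure-adjusted rate stand in for timing?** The SAP formula is rate = events / patient-years × 100, with a year of 336 days (48 weeks).

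*Complete follow-up.* Assume 96 patients, 240 weeks each, 48 events.
- Patient-years = 96 × 240 × 7 / 336 = 480.
- Pooled rate = 48 / 480 × 100 = 10.0.
- Each 48-week block holds 96 × 48 × 7 / 336 = 96 patient-years.

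| Pattern | Events per 48-week block | Rate per block | Pooled rate |
|---|---|---|---|
| All early | 48, 0, 0, 0, 0 | 50, 0, 0, 0, 0 | 10.0 |
| Even | 9.6 in each | 10, 10, 10, 10, 10 | 10.0 |
| All late | 0, 0, 0, 0, 48 | 0, 0, 0, 0, 50 | 10.0 |

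The equality of the pooled rates does not depend on the assumed counts.

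*With dropout.* Assume half the patients leave at Week 120, unrelated to the event, and one event per affected patient. Mean exposure = (240 + 120) / 2 = 180 weeks = 3.75 SAP years.
- Event A, 20% risk, all in the first 24 weeks: incidence 20%, rate 0.20 / 3.75 × 100 = 5.3.
- Event B, 2% of the starting cohort per 24 weeks if all stayed: incidence 10% + ½ × 10% = 15%, rate 0.15 / 3.75 × 100 = 4.0.
- Event C, 15% risk, all in the first 24 weeks: incidence 15%, rate 0.15 / 3.75 × 100 = 4.0.

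A and B now differ, but B and C share a row although one accrues throughout and the other is confined to the start.

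**3. Could the protocol table be produced with the SAP's visit windows?** SAP section 5.1 derives visits in by-visit summaries from the section 6.1 windows. As printed, the Week 12 window opens at Day 42, and no window lies between the end of Week 192 (Day 1386) and the start of Week 216 (after Day 1470).
- Days 2 to 41: 40 days.
- Days 1387 to 1470: 84 days.
- Unassigned: 124 of 240 × 7 = 1680 days, or 7.4%.

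Events with onset on those days would fall in no visit.

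**The case against.** A reader might infer that the study has no analysis of when safety events occur and that the protocol's table was deleted with nothing in its place. The documents do not support that. The endpoint also covers laboratory abnormalities, and laboratory values and shift tables remain by visit, as do vital signs and ECG. An exposure-adjusted rate that is not in protocol section 10.4.5.1 was added. Onset dates are recorded (protocol section 8.3) and would be listed.

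Nor does the SAP say that the table is removed. It overrides the protocol only where the two conflict, and silence is arguably not conflict, so the protocol table may still apply. That is fair, but it leaves unclear which text governs, and producing the table from the SAP's windows would lose the days shown above.

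Two further limits stand. The exact equality of early, even and late patterns needs complete follow-up, whereas the plan expects departures for commercial drug and sponsor termination (SAP section 5.2). And all patients have had ataluren before (protocol section 4.2); in Study 007e, for example, the median was 22 weeks (protocol section 2.2.3.2.3). Week 1 is therefore not first exposure, and onset intervals cannot cleanly separate early-exposure effects from long-exposure effects. In a single-arm study of a progressive disease, late intervals also reflect age, progression and selective retention.

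**Conclusion.** The point holds for adverse events. Followed as written, SAP section 5.7.1 leaves the AE timing component of the primary endpoint with no aggregate summary, and section 7 does not disclose it. This is an unrecorded omission, not a stated removal.

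Its size is descriptive. No hypothesis test is affected, and the calculations are illustrations on assumed figures, not predictions for this trial. They establish only that the pooled rows can coincide for quite different onset patterns under complete follow-up, and that with dropout they may differ without revealing timing. Because timing is part of the primary endpoint and the data exist, the SAP should be corrected.

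**What to change.** Add to SAP section 5.7.1 TEAE incidence and exposure-adjusted rates by onset-day interval, for example 48-week blocks, with patients and person-time at risk in each interval as denominators. Present them at least overall and for serious, Grade 3 or higher, and hepatic, renal and adrenal events. Adrenal events are among those singled out in protocol section 10.4.5.1, but the matching SAP item names only hepatic and renal.

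Define the intervals by onset day, not by the section 6.1 windows. Keep the 336-day year so that the blocks add up to the pooled row, and state how events in the 6 weeks after the last dose are assigned, since SAP patient-years count only days on drug.

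Record in section 7 that these tables replace the protocol's by-visit table. The minimum alternative is to list the omission there and justify it. The text accompanying the tables should note prior exposure and the effects of age, progression and retention on late intervals.

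The cost is one more table family from dates already collected, with no new data or design change. With up to about 96 patients some cells will be sparse, particularly beyond Week 240, where only the Canadian extension contributes scheduled visits.

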10.4.5.2. Laboratory Data

Hematological, serum biochemistry, adrenal laboratories, and urine data and their changes (only for continuous laboratory parameters) from baseline will be summarized by visit. Hematological, serum biochemistry, adrenal laboratories, and urine data will be graded according to CTCAE severity grade when applicable. For parameters for which a CTCAE scale does not exist, the frequency of patients with values below, within, and above the normal ranges will be summarized. Summary tables will be presented for each relevant assay to show the number of patients by severity grade with corresponding percentages. Subjects will be characterized only once for a given assay, based on their worst severity grade observed during the time period of interest.

Shift tables for hematology, serum biochemistry, adrenal laboratories, and urine data will also be presented showing change in CTCAE severity grade from baseline to each visit. For parameters for which a CTCAE scale does not exist, shift tables will be presented showing change in results from baseline (normal, low and high [or abnormal]) to each visit (normal, low and high [or abnormal]).

Separate listings and tables will be created for parameters for assessment of adrenal, hepatic, and renal monitoring based on the conditions listed in Section 6.3.

10.4.5.3. Physical Findings

Physical findings (weight, physical examination data, systolic and diastolic blood pressure, radial pulse rate, and body temperature) will be listed and summarized by visit. Where appropriate, changes from baseline at each visit will be summarized and tested using the paired t-test or a nonparametric alternative.

10.4.6. Secondary Variables

10.4.6.1. 6-Minute Walk Test

The distance walked at each visit and the change from baseline in the distance walked at each

postbaseline visit, as obtained from the 6MWT, will be summarized descriptively. Only the results of the patient's best valid test at each visit will be included in the analysis. Changes from baseline in 6MWD at each postbaseline visit will be analyzed using paired t-tests. All data from the 6MWTs, valid or invalid, will be listed by patient and visit, with invalid results flagged.

The 6MWD at each visit will be converted into a percent-predicted 6MWD value through the use of a relevant reference equation. The percent-predicted 6MWD value at each visit and the change from baseline in the percent-predicted 6MWD value will be summarized descriptively. Only the results of the patient's best valid test at each visit will be included in the analysis. Changes from baseline at each postbaseline visit will be analyzed using paired t-tests. All percent-predicted 6MWD values, valid or invalid, will be listed by patient and visit, with invalid results flagged.

